6.3.8. Dose Modification

Pembrolizumab will be withheld for drug-related haematological and non-haematological of toxicity \geq Grade 3 including laboratory abnormalities, and severe or life-threatening AEs as per Table 7 below.

Toxicity	Hold Treatment For Grade	Timing for Restarting Treatment	Treatment Discontinuation
Diarrhoea/Colitis	2-3	Toxicity resolves to Grade 0-1.	Toxicity does not resolve within 12 weeks of last dose or inability to reduce corticosteroid to 10 mg or less of prednisone or equivalent per day within 12 weeks.
	4	Permanently discontinue	Permanently discontinue
AST, ALT, or	2	Toxicity resolves to Grade 0-1	Toxicity does not resolve within 12 weeks of last dose.

Increased Bilirubin	3-4	Permanently discontinue (see exception below) ¹	Permanently discontinue
Type 1 diabetes mellitus (if new onset) or Hyperglycemia	T1DM or 3-4	Hold pembrolizumab for new onset Type 1 diabetes mellitus or Grade 3-4 hyperglycemia associated with evidence of beta cell failure.	Resume pembrolizumab when participants are clinically and metabolically stable.
Hypophysitis	2-4	Toxicity resolves to Grade 0-1. Therapy with pembrolizumab can be continued while endocrine replacement therapy is instituted	Toxicity does not resolve within 12 weeks of last dose or inability to reduce corticosteroid to 10 mg or less of prednisone or equivalent per day within 12 weeks.
Hyperthyroidism	3	Toxicity resolves to Grade 0-1	Toxicity does not resolve within 12 weeks of last dose or inability to reduce corticosteroid to 10 mg or less of prednisone or equivalent per day within 12 weeks.
	4	Permanently discontinue	Permanently discontinue
Hypothyroidism		Therapy with pembrolizumab can be continued while thyroid replacement therapy is instituted	Therapy with pembrolizumab can be continued while thyroid replacement therapy is instituted.
Infusion Reaction	3-4	Permanently discontinue	Permanently discontinue
Pneumonitis	2	Toxicity resolves to Grade 0-1	Toxicity does not resolve within 12 weeks of last dose or inability to reduce corticosteroid to 10 mg or less of prednisone or equivalent per day within 12 weeks.
	3-4	Permanently discontinue	Permanently discontinue
	3-4	Permanently discontinue	Permanently discontinue
Renal Failure or Nephritis	2	Toxicity resolves to Grade 0-1	Toxicity does not resolve within 12 weeks of last dose or inability to reduce corticosteroid to 10 mg or less of prednisone or equivalent per day within 12 weeks.

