All Other Drug-Related Toxicity²	3 or Severe	Toxicity resolves to Grade 0-1	Toxicity does not resolve within 12 weeks of last dose or inability to reduce corticosteroid to 10 mg or less of prednisone or equivalent per day within 12 weeks.
	4	Permanently discontinue	Permanently discontinue

Note: Permanently discontinue for any severe or Grade 3 drug-related AE that recurs or any life-threatening event.
¹ For participants with liver metastasis who begin treatment with Grade 2 AST or ALT, if AST or ALT increases by greater than or equal to 50% relative to baseline and lasts for at least 1 week then participants should be discontinued.
² Participants with intolerable or persistent Grade 2 drug-related AE may hold study medication at physician discretion. Permanently discontinue study drug for persistent Grade 2 adverse reactions for which treatment with study drug has been held, that do not recover to Grade 0-1 within 12 weeks of the last dose.

Table 8: Dose modification guidelines for drug-related adverse events

If the toxicity does not resolve to Grade 0-1 within 12 weeks after last infusion, trial treatment should be discontinued at the discretion of the investigator. Participants with a laboratory adverse event still at Grade 2 after 12 weeks may continue treatment in the trial only if asymptomatic and controlled. For information on the management of adverse events, see section 7.

Participants who experience a recurrence of the same severe or life-threatening event at the same grade or greater with re-challenge of pembrolizumab should be discontinued from trial treatment.

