6.5. Rescue Medications & Supportive Care

6.5.1. Supportive Care Guidelines

Participants should receive appropriate supportive care measures as deemed necessary by the treating investigator including but not limited to the items outlined below:

6.5.1.1. Diarrhoea:

Participants should be carefully monitored for signs and symptoms of:

- Enterocolitis (diarrhoea, abdominal pain, blood or mucus in stool, with or without fever)
- Bowel perforation (peritoneal signs and ileus).

In symptomatic participants, infectious etiologies should be ruled out, and if symptoms are persistent and/or severe, endoscopic evaluation should be considered.

- In participants with severe enterocolitis (Grade 3):
 - Pembrolizumab will be **permanently discontinued** and treatment with systemic corticosteroids should be initiated at a dose of 1 to 2 mg/kg/day of prednisone or equivalent. When symptoms improve to Grade 1 or less, corticosteroid taper should be started and continued over at least 1 month.
- In participants with moderate enterocolitis (Grade 2):
 - Pembrolizumab should be **withheld** and anti-diarrhoeal treatment should be started. If symptoms are persistent for more than one week, systemic corticosteroids should be initiated (e.g., 0.5 mg/kg/day of prednisone or equivalent). When symptoms improve to Grade 1 or

less, corticosteroid taper should be started and continued over at least 1 month. Guidelines for continuing treatment with pembrolizumab can be found in Appendix 5.

- All participants who experience diarrhoea should be advised to drink liberal quantities of clear fluids. If sufficient oral fluid intake is not feasible, fluid and electrolytes should be substituted via IV infusion.

6.5.1.2. Nausea/vomiting:

Nausea and vomiting should be treated aggressively, and consideration should be given in subsequent cycles to the administration of prophylactic antiemetic therapy according to standard institutional practice. Participants should be strongly encouraged to maintain liberal oral fluid intake.

6.5.1.3. Anti-infectives:

Participants with a documented infectious complication should receive oral or IV antibiotics or other anti-infective agents as considered appropriate by the treating investigator for a given infectious condition, according to standard institutional practice.

6.5.1.4. Immune-related adverse events:

Please see Section 6.5.2 below regarding diagnosis and management of adverse experiences of a potential immunologic etiology.

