7.4. Definitions of Evidence of Clinical Interest (ECI)

Selected non-serious and serious adverse events can also be classified as Events of Clinical Interest (ECI) and must be reported as described in section 7.6.

The following ECIs for this study must be reported to the Sponsor within 24hrs of learning of the event:

1. An overdose of pembrolizumab, as defined in Section 7.7 that is not associated with clinical symptoms or abnormal laboratory results.
2. A Drug induced liver injury (DILI) defined as elevated AST or ALT lab value that is greater than or equal to 3X the upper limit of normal

AND / OR

An elevated total bilirubin lab value that is greater than or equal to 2X the upper limit of normal **AND / OR**

An alkaline phosphatase lab value that is less than 2X the upper limit of normal, as determined by way of protocol-specified laboratory testing or unscheduled laboratory testing.

NOTE: These events will also be reported to MSD by the sponsor.

3. Any AEs identified in the below table can be classified as immune-related events of clinical interest. A detailed narrative of the event should be recorded as an ECI as described in section 7.6:

Pneumonitis - (deemed as an ECI if ≥ Grade 2 to be reported through the AE reporting pathway)		
Acute interstitial Pneumonitis	Interstitial Lung Disease	Pneumonitis
Colitis - (deemed as an ECI if ≥ Grade 2 or any grade resulting in dose modification or use of systemic steroids to treat the AE to be reported through the AE reporting pathway)		
Intestinal Obstruction	Colitis	Colitis microscopic
Enterocolitis	Enterocolitis hemorrhagic	Gastrointestinal perforation
Necrotising colitis	Diarrhoea	
Endocrine - (deemed as an ECI if ≥ Grade 3 or ≥ Grade 2 and resulting in dose modification or use of systemic steroids to treat the AE and will be reported through the AE reporting pathway)		
Adrenal Insufficiency	Hyperthyroidism	Hypophysitis
Hypopituitarism	Hypothyroidism	Thyroid disorder
Thyroiditis	Hyperglycemia, if ≥Grade 3 and associated with ketosis or metabolic acidosis (DKA)	
Endocrine (deemed as an ECI and will be reported through the AE reporting pathway)		
Type 1 diabetes mellitus (if new onset)		
Hematologic - (deemed as an ECI if ≥ Grade 3 or any grade resulting in dose modification or use of systemic steroids to treat the AE and will be reported through the AE reporting pathway)		
Autoimmune haemolytic anaemia	Aplastic anaemia	Thrombotic thrombocytopenic purpura

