APPENDIX 4: Identification, evaluation and management of ECIs

ECI	Grade	Action to be taken	Supportive Care
Pneumonitis –	Grade 1 (Asymptomatic)	
 No action 	
 Intervention not indicated
	Grade 2	
 Report as ECI within 24 hours Withhold pembrolizumab, may restart if Grade 1 or resolved within 12 weeks Consider bronchoscopy and biopsy/BAL, ID Consult and frequent chest x-ray for monitoring. Conduct in person evaluation twice a week 	
 1-2mg/kg/day prednisone or equivalent. Symptoms grade 1 or less, initiate steroid taper for no less than 4 weeks. Permanently discontinue pembrolizumab if dose cannot be reduced to 10mg prednisone or less or equivalent per day within 12 weeks.
	Grade 3 and 4	
 Report as ECI within 24 hours Discontinue pembrolizumab Hospitalize patient Bronchoscopy with biopsy and/or BAL is recommended. 	
 methylprednisolone 125mg IV. Symptoms grade 1 or less initiate steroid taper for no less than 4 weeks 
 Prednisone 1 to 2 mg/kg/day or dexamethasone 4mg every 4 hours If IV steroids do not reduce initial symptoms within 48-72 hours treat with additional anti-inflammatory measures. At symptom relief discontinue anti-inflammatory and start steroid taper over 45-60 days. If symptoms worsen during this period refer to ECI guidance document v5.0.
	
 1st episode - May increase dosing interval by one week in subsequent cycles 2nd episode of - Pneumonitis Permanently discontinue pembrolizumab if upon re-challenge patient develops Pneumonitis ≥ Grade 2 		
Colitis	Grade 1 (Asymptomatic)	
 No action 	
 Intervention not indicated
	Grade 2 (For grade 2 diarrhoea that persists > 3 days)	
 Report as ECI within 24 hours Withhold pembrolizumab, may restart if Grade 1 or resolved within 12 weeks Symptomatic treatment Consider GI consult & endoscopy to rule out colitis 	
 Prednisone 1-2mg/kg/day or equivalent Symptoms grade 1 or less, initiate steroid taper for no less than 4 weeks. Permanently discontinue pembrolizumab if dose cannot be reduced to 10mg or less of prednisone or equivalent per days within 12 weeks. If symptoms worsen or persist >1 week treat as grade 3.

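### Appendix 4 ties its Grade 2 diarrhoea instructions to persistence beyond 3 days, while sections 6.3.8, 6.5.1.1, 6.5.2 and 7.4 hold or classify at Grade 2 with no duration; the steroid-start timing also conflicts

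*Combined protocol and SAP*

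**What the plan says.** Six places in the combined protocol and SAP bear on Grade 2 diarrhoea.

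- **Appendix 4, Colitis.** The Grade 2 row is headed "Grade 2 (For grade 2 diarrhoea that persists > 3 days". Its actions are to report as an ECI within 24 hours, to treat symptoms and "Withhold pembrolizumab, may restart if Grade 1 or resolved within 12 weeks"; its supportive-care column lists prednisone. The other rows are Grade 1 (no action), Grade 3 and Grade 4.
- **Section 6.3.8, dose-modification table.** The row reads "Diarrhoea/Colitis 2-3 Toxicity resolves to Grade 0-1", where 2-3 are the grades at which treatment is held. No duration is attached. The caption, "Dose modification guidelines for drug-related adverse events", limits the table to drug-related events.
- **Section 6.5.1.1, Grade 2 enterocolitis.** "Pembrolizumab should be withheld and anti-diarrhoeal treatment should be started". A waiting period applies to steroids only: "If symptoms are persistent for more than one week, systemic corticosteroids should be initiated".
- **Section 6.5.2, immune-mediated colitis.** Corticosteroids are given and pembrolizumab is withheld at Grade 2 or 3, with no duration stated.
- **Section 6.5.2, irECI paragraph.** A symptomatic immune-related ECI stops pembrolizumab at once pending evaluation. The reader is sent to Appendix 4 once the event is judged associated with the drug.
- **Section 7.4.** "Colitis - (deemed as an ECI if ≥ Grade 2 or any grade resulting in dose modification". The list under this entry includes diarrhoea, and no duration is attached.

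**The concern.** Appendix 4 is the management table that section 6.5.2 directs sites to. If its Grade 2 row starts only after 3 days while the other sections start at Grade 2, the answer to three questions depends on the page opened: when the hold begins, when the event is to be reported as an ECI, and when steroids begin.

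ECI status has consequences beyond recording. Section 6.4.2 prohibits glucocorticoids except for an ECI of suspected immunologic cause, or at physiologic doses after consultation. Section 7.4 also requires assessment for possible ECIs before each dose, so a site can meet the question on a dosing day. With 15-24 sites, differing readings would produce differing practice on the same kind of event.

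This point concerns when the instructions begin. It does not address steroid doses or the handling of Grade 3 colitis.

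**Working it through.** No arithmetic applies, and the plan states no figure to reproduce. The check follows one case, drug-related Grade 2 diarrhoea that stays at Grade 2, through each section. Day 1 is the day of onset, so persistence beyond 3 days begins on day 4.

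| Place | Days 1-3 | Days 4-7 | Beyond one week |
|---|---|---|---|
| Appendix 4, Colitis, Grade 2 | No row applies | Withhold, report as ECI, prednisone | Treat as Grade 3 |
| 6.3.8 (drug-related events) | Hold | Hold | Hold |
| 6.5.1.1 (Grade 2 enterocolitis) | Withhold; steroids not yet started | Withhold; steroids not yet started | Withhold; start steroids |
| 6.5.2 (immune-mediated colitis) | Withhold; corticosteroids | Withhold; corticosteroids | Withhold; corticosteroids |
| 6.5.2 (symptomatic irECI) | Stop and evaluate | Stop and evaluate | Stop and evaluate |
| 7.4 (diarrhoea listed under Colitis) | ECI | ECI | ECI |

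1. **Hold.** The mismatch is confined to the first 3 days. Sections 6.3.8, 6.5.1.1 and 6.5.2 all hold then, and Appendix 4 gives no instruction. From day 4 all of them hold.
2. **ECI.** Section 7.4 classifies the event from the first day at Grade 2. The reporting instruction in Appendix 4 sits under the 3-day condition. The two differ on days 1-3, and for the whole of any Grade 2 episode that lasts 3 days or less.
3. **Steroid start.** This conflict does not rest on silence. On day 5, Appendix 4 lists prednisone, 6.5.1.1 has not yet reached its trigger, and the colitis paragraph of 6.5.2 has no waiting period.
4. **Which text governs.** Nothing states an order of precedence. For continuing treatment after Grade 2 enterocolitis, 6.5.1.1 refers to an Appendix 5, but the appendices end at 4.

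**The case against.** A reader might infer that a patient with new Grade 2 diarrhoea on dosing day is dosed under Appendix 4 and held under 6.3.8. The documents do not support that. Appendix 4 is silent on the first 3 days and never says to dose. A site that reaches it through section 6.5.2 has already been told to stop pembrolizumab for a symptomatic irECI, and 7.4 lists Grade 2 diarrhoea in that group. No section permits the dose. It would also be too broad to say that 6.3.8 holds for every Grade 2 diarrhoea, because its caption covers drug-related events only.

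A reader might also try to count affected doses, for instance by applying 3/21 of a cycle to an assumed incidence. That count has no basis here. Section 1.2.2 names diarrhoea among common adverse events but gives no Grade 2 rate and says most events were low grade. The fraction depends on how long episodes last, and the schedule allows ±3 days around each cycle visit.

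Other limits stand. The 3-day wording can be read as qualifying diarrhoea only, leaving other Grade 2 colitis outside the condition. The colitis paragraph of 6.5.2 defers to guidelines above it, which could be read as bringing in the one-week wait. Adverse events are recorded with their grade in any case (section 7.2), and the planned toxicity comparison uses grade 3-5 events (section 8.5), so the ECI status of a short Grade 2 episode enters no planned test.

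These points narrow the concern without removing it. Appendix 4 applies to events judged associated and 6.3.8 to drug-related events, so the two address the same patient with different start conditions. None of the readings above reconciles the steroid timing in Appendix 4 with that in 6.5.1.1.

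**Conclusion.** The inconsistency is real and limited. Appendix 4 alone makes the Grade 2 diarrhoea hold and ECI instruction depend on persistence beyond 3 days, and it leaves the first 3 days without an instruction. Steroid-start timing conflicts outright on days 4-7 between Appendix 4 and 6.5.1.1, and 6.5.2 states no wait at all.

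The practical effect is inconsistent instructions to sites on Grade 2 management and ECI reporting. Its frequency cannot be estimated from the documents. No effect on the sample size or the primary analysis is shown. The comparison of 6.5.1.1 and 6.5.2 with the other sections assumes that the Grade 2 diarrhoea is the enterocolitis or colitis they describe; the comparison of Appendix 4 with 6.3.8 and 7.4 needs no such assumption, because 6.3.8 names "Diarrhoea/Colitis" and 7.4 lists diarrhoea. This should be corrected because it bears on patient management and costs little to fix.

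**What to change.** Reconcile sections 6.3.8, 6.5.1.1, 6.5.2 (both the colitis and the irECI paragraphs), 7.4 and Appendix 4, so that a reader of any one of them finds the same answer on when the hold, the ECI classification and the steroid start apply for Grade 2 diarrhoea. The three need not share a trigger. The amended text should also cover Grade 2 diarrhoea of 3 days or less explicitly, and the Appendix 5 reference in 6.5.1.1 should point to an appendix that exists. The clinical leads choose the rules; this review proposes none.

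The cost is a wording amendment to the affected tables and paragraphs, with no added assessments and no change to the sample size or analysis.

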6.5.3. Supportive Care Guidelines for Pneumonitis

Participants with symptomatic pneumonitis should immediately stop receiving pembrolizumab and have an evaluation. The evaluation may include bronchoscopy and pulmonary function tests to rule out other causes such as infection. If the participant is determined to have study drug associated pneumonitis, the suggested treatment plan is detailed in Table 10.

Study drug associated pneumonitis	Withhold/Discontinue pembrolizumab?	Supportive Care
Grade 1 (asymptomatic)	No action	Intervention not indicated
Grade 2	Withhold pembrolizumab, may return to treatment if improves to Grade 1 or resolves within 12 weeks. Second episode of pneumonitis – discontinue pembrolizumab if upon re-challenge the participant develops a second episode of Grade 2 or higher pneumonitis.	Consider pulmonary consultation with bronchoscopy and biopsy/BAL. Conduct an in person evaluation approximately twice per week Consider frequent Chest X-ray as part of monitoring Treat with systemic corticosteroids at a dose of 1 to 2 mg/kg/day prednisone or equivalent. When symptoms improve to Grade 1 or less, steroid taper should be started and continued over no less than 4 weeks. Consider antibiotics
Grade 3 and Grade 4	Discontinue pembrolizumab	Hospitalise participant

		
Bronchoscopy with biopsy and/or BAL is recommended.
 
Immediately treat with intravenous steroids (methylprednisolone 125 mg IV). When symptoms improve to Grade 1 or less, a high dose oral steroid (prednisone 1 to 2 mg/kg once per day or dexamethasone 4 mg every 4 hours) taper should be started and continued over no less than 4 weeks.
 
If IV steroids followed by high dose oral steroids does not reduce initial symptoms within 48 to 72 hours, treat with additional anti-inflammatory measures. Discontinue additional anti-inflammatory measures upon symptom relief and initiate a prolonged steroid taper over 45 to 60 days. If symptoms worsen during steroid reduction, initiate a re-tapering of steroids starting at a higher dose of 80 or 100mg followed by a more prolonged taper and administer additional anti-inflammatory measures, as needed. Add prophylactic antibiotics for opportunistic infections. The use of infliximab may be indicated as appropriate.

--	--	--

Table 10: Recommended Approach to Handling Pneumonitis

For Grade 2 pneumonitis that improves to \leq Grade 1 within 12 weeks, the following rules should apply:

- First episode of pneumonitis

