Endocrine – Hypophysitis or other symptomatic endocrinopathy	Grade 1 (Asymptomatic)	
 No action 	Intervention not indicated
	Grade 2 – 4	
 Report as ECI if appropriate - see ECI v5 guidance. Withhold pembrolizumab Rule out infection and sepsis. Monitor thyroid function until returned to baseline. Consider pituitary gland imaging Hypophysitis with clinically significant adrenal insufficiency and hypotension, dehydration, and electrolyte abnormalities (such as hyponatremia and hyperkalemia) constitutes adrenal crisis. Consider endocrinologist consult. 	
 Prednisone 40mg p.o. or equivalent per day. Symptoms grade 1 or less initiate steroid taper for no less than 4 weeks. Replacement of appropriate hormones may be required. Permanently discontinue pembrolizumab if dose cannot be reduced to prednisone 10mg or less or equivalent per day within 12 weeks.
Type 1 Diabetes Mellitus and ≥ Grade 3 hyperglycaemia	Type 1 Diabetes Mellitus and ≥ grade 3 hyperglycaemia	
 Report as ECI if appropriate see Table 11 Hold pembrolizumab if new onset of diabetes or grade 3-4 hyperglycaemia with evidence of beta cell failure. Consultation with endocrinologist Consider islet cell antibodies and antibodies to GAD, IA-2 ZnT8 and insulin. 	
 Insulin replacement therapy is recommended for Type I diabetes mellitus and for Grade 3-4 hyperglycaemia associated with metabolic acidosis or ketonuria. Evaluate patients with serum glucose and a metabolic panel, urine ketones, glycosylated haemoglobin, and C-peptide.
Hematologic	Grade 1 (Asymptomatic)	
 No action 	
 Intervention not indicated
	Grade 2	
 Report as ECI within 24 hours Withhold pembrolizumab, may restart if Grade 1 or resolved within 12 weeks Consider Haematology consultation 	
 Prednisone 1-2mg/kg daily Permanently discontinue pembrolizumab if dose cannot be reduced to prednisone 10mg or less or equivalent per day within 12 weeks.

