	Grade 3	
 Report as ECI within 24 hours Withhold pembrolizumab, may restart if Grade 1 or resolved within 12 weeks Recommend Haematology consultation 	
 IV methylprednisone 125mg or Prednisone 1-2mg/kg p.o. (or equivalent) as appropriate. Permanently discontinue pembrolizumab if corticosteroid dose cannot be reduced to prednisone 10mg or less or equivalent per day within 12 weeks.
	Grade 4	
 Report as ECI within 24 hours Discontinue pembrolizumab Recommend Haematology consultation 	
 IV methylprednisone 125mg or Prednisone 1-2mg/kg p.o. (or equivalent) as appropriate.
Hepatic – Drug induced Liver Injury (DILI). Please refer to ECI guidance for definitions of (DILI)	Grade 1 (Asymptomatic)	
 No action 	
 Intervention not indicated
	Grade 2	
 Report as ECI within 24 hours Withhold Pembrolizumab if AST or ALT >3.0 to 5.0 X ULN and/or total bilirubin is >1.5 to 3.0 X ULN Monitoring Liver function until values return to baseline 	
 0.5-1mg/kg/day methylprednisone 125mg or oral equivalent. LFT grade 1 or less initiate steroid taper for no less than 4 weeks. Consider prophylactic antibiotics and resume pembrolizumab. Permanently discontinue pembrolizumab if dose cannot be reduced to prednisone 10mg or less or equivalent per day within 12 weeks. Permanently discontinue pembrolizumab for patients with liver mets who begin treatment with grade 2 elevation of AST or ALT and AST or ALT increase ≥50% relative to baseline and lasts ≥ 1 week.
	Grade 3	
 Report as ECI within 24 hours Discontinue pembrolizumab if AST or ALT > 5.0 X ULN and/or total bilirubin is >3.0 X ULN Consider consultation and biopsy to establish etiology 	
 High dose IV glucocorticosteroids for 24-48hours. Symptoms grade 1 or less initiate steroid taper for no less than 4 weeks prednisone 1 to 2 mg/kg/day or dexamethasone 4mg every 4 hours. If serum transaminase levels do not decrease or symptoms worsen please refer to additional guidance in the ECI guidance document.

			
 Permanently discontinue pembrolizumab if dose cannot be reduced to prednisone 10mg or less or equivalent per day within 12 weeks.

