	Grade 2	
 Report as ECI within 24 hours Withhold Pembrolizumab 	
 1-2mg/kg of prednisone daily. Permanently discontinue pembrolizumab is if dose cannot be reduced to prednisone 10mg or less or equivalent per day within 12 weeks.
	Grade 3 and 4	
 Report as ECI within 24 hours Discontinue Pembrolizumab Renal consultation and biopsy as appropriate 	
 1-2mg/kg of prednisone daily. Symptoms grade 1 or less initiate steroid taper for no less than 4 weeks.
Skin – Rash and pruritus	Grade 1 (Asymptomatic)	
 No action 	
 Intervention not indicated
	Grade 2	
 Symptomatic treatment 	
 Topical glucocorticosteroids or urea containing cream in combination with oral anti-pruritics Treatment with oral steroids at PIs discretion
	Grade 3	
 Report as ECI within 24 hours Withhold Pembrolizumab Consider dermatology consult & biopsy for diagnosis. 	
 1mg/kg/day prednisone or equivalent or dexamethasone 4mg 4xdaily Symptoms grade 1 or less, initiate steroid taper for no less than 4 weeks. Permanently discontinue pembrolizumab is if dose cannot be reduced to prednisone 10mg or less or equivalent per day within 12 weeks.
	Grade 4	
 Report as ECI within 24 hours Discontinue pembrolizumab Dermatology consultation Consider biopsy for diagnosis & clinical photographs 	
 Initiate steroids starting with 1-2mg/kg prednisone or equivalent.. Symptoms grade 1 or less, initiate steroid taper for no less than 4 weeks.
Skin – Dermatitis exfoliative, erythema multiforme, Stevens Johnson	Grade 1 (Asymptomatic)	
 No action 	
 Intervention not indicated
	Grade 2	
 Report as ECI within 24 hours Symptomatic treatment 	
 Topical glucocorticosteroids or urea-containing cream in combination with oral anti-pruritics. Treatment

syndrome, toxic epidermal necrolysis		
 Withhold pembrolizumab 	with oral steroids at PIs discretion

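### Section 6.5.1.1 contradicts Sections 6.3.8, 6.5.2 and Appendix 4 on pembrolizumab at a first Grade 3 enterocolitis, and the colitis and hepatic Grade 2 steroid instructions do not give one dose

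*Combined protocol and SAP*

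**What the plan says.** **Pembrolizumab at Grade 3.** The severe-enterocolitis bullet of Section 6.5.1.1 discontinues pembrolizumab permanently. The Diarrhoea/Colitis row of the table in Section 6.3.8 holds it for Grades 2 and 3, allows restart at Grade 0-1, and stops it permanently at Grade 4. It also stops treatment if the toxicity has not resolved, or steroids cannot be reduced to 10 mg or less of prednisone, within 12 weeks. The note under that table requires permanent discontinuation for a Grade 3 event that recurs or a life-threatening event. The colitis paragraph of Section 6.5.2 and the Grade 3 colitis row of Appendix 4 both withhold.

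**Steroids at Grade 2 colitis.** After anti-diarrhoeal treatment, Section 6.5.1.1 says: "If symptoms are persistent for more than one week, systemic corticosteroids should be initiated (e.g., 0.5 mg/kg/day of prednisone or equivalent". The Grade 2 colitis row of Appendix 4 is labelled "For grade 2 diarrhoea that persists > 3 days", gives "Prednisone 1-2mg/kg/day or equivalent", and sends symptoms that worsen or last more than a week to the Grade 3 row.

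**Steroids at Grade 3 colitis.** Section 6.5.1.1 gives prednisone 1 to 2 mg/kg/day. Appendix 4 gives methylprednisolone 125 mg IV, followed by prednisone 1 to 2 mg/kg/day or dexamethasone.

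**Hepatic Grade 2.** The Appendix 4 line is "0.5-1mg/kg/day methylprednisone 125mg or oral equivalent".

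**Routing.** Section 6.5.1.4 says: "Please see Section 6.5.2 below regarding diagnosis and management of adverse experiences of a potential immunologic etiology". Section 6.5.2 then refers drug-associated irECIs to Appendix 4.

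**The concern.** These texts cover the same events. Section 7.4 lists enterocolitis and diarrhoea under its colitis heading, and the 6.3.8 row covers diarrhoea and colitis together. A site that opens Section 6.5.1.1 and a site that opens Appendix 4 can therefore treat the same patient differently and both be following the protocol. At a first Grade 3 episode, the difference is whether the patient may ever resume pembrolizumab. At Grade 2, it is when steroids start and at what dose. For hepatic Grade 2, the instruction cannot be followed as written, because it gives two quantities and no rule for combining or choosing between them. The stake is patient safety and consistent care across the planned 15 to 24 sites.

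**Working it through.** The plan has no figure of its own to reproduce here. The check sets the texts side by side and adds dose arithmetic. The documents give no body weights, so 50, 70 and 100 kg are assumed, and no conversion between steroids is used.

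**1. Pembrolizumab, first Grade 3 episode**

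| Text | Instruction |
|---|---|
| 6.5.1.1 | discontinue permanently |
| 6.3.8 table | hold; restart at Grade 0-1 |
| 6.5.2, colitis | withhold |
| Appendix 4, colitis Grade 3 | withhold |

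One text discontinues and three hold. For a recurrent Grade 3 event, the 6.3.8 note agrees with 6.5.1.1, so the conflict is confined to the first episode.

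**2. Steroids, Grade 2 colitis**

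| Duration of symptoms | 6.5.1.1 | Appendix 4 |
|---|---|---|
| More than 3 days, up to 1 week | no steroid yet | prednisone 1-2 mg/kg/day |
| More than 1 week | e.g. 0.5 mg/kg/day | Grade 3 regimen: 125 mg IV, then 1-2 mg/kg/day prednisone or dexamethasone |

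The Appendix 4 row states no separate day for starting steroids; the table takes the row's own duration label as its start.

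- At 70 kg, the 6.5.1.1 example is 0.5 × 70 = 35 mg/day.
- The Appendix 4 Grade 2 dose is 1 × 70 = 70 to 2 × 70 = 140 mg/day.
- The ratio is 1/0.5 = 2 to 2/0.5 = 4. It compares doses that apply at different times. Beyond one week the contrast is sharper: one text begins an example low dose, and the other starts with 125 mg IV.

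**3. Hepatic Grade 2**

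Inputs are 0.5-1 mg/kg/day and 125 mg, from the single Appendix 4 line. The line gives the 125 mg no route or frequency. The ratios below hold only if it is read as a daily dose.

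| Weight | 0.5-1 mg/kg | 125 mg ÷ upper end | 125 mg ÷ lower end |
|---|---|---|---|
| 50 kg | 25-50 mg | 125/50 = 2.5 | 125/25 = 5.0 |
| 70 kg | 35-70 mg | 125/70 = 1.79 | 125/35 = 3.57 |
| 100 kg | 50-100 mg | 125/100 = 1.25 | 125/50 = 2.5 |

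On that reading, the two doses coincide only between 125/1 = 125 kg and 125/0.5 = 250 kg. By contrast, the haematologic Grade 3 and 4 rows of the same table offer 125 mg IV and a weight-based oral dose as alternatives joined by an explicit or. The hepatic line has no such link.

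**The case against.** These are guidelines, and Section 6.5.1 leaves supportive measures to the treating investigator. Section 6.5.2 asks for any Grade 2 or higher irAE to be discussed at once with the CI or designee. The routing from 6.5.1.4 through 6.5.2 to Appendix 4 suggests that Appendix 4 governs drug-associated events. The 0.5 mg/kg/day in 6.5.1.1 is only an example. All of this stands and lowers the risk. None of it says which text prevails, and 6.5.1.1 itself names enterocolitis, steroids and pembrolizumab.

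A reader might infer more than the documents support:

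- **That 125 mg belongs only to Grade 3 and 4, so the hepatic line is an overdose.** The other five places that give 125 mg are indeed Grade 3 or 4 entries, such as pneumonitis in Section 6.5.3: "Immediately treat with intravenous steroids (methylprednisolone 125 mg IV". But Appendix 4 sends persistent Grade 2 colitis to the regimen that starts with 125 mg. Other Grade 2 rows also exceed 0.5-1 mg/kg: haematologic has "Prednisone 1-2mg/kg daily" and renal has "1-2mg/kg of prednisone daily". The fault shown is an unlinked pair of doses.
- **That 6.5.2 points back to 6.5.1.1.** Its colitis paragraph refers to guidelines above, but the same phrase is used for pneumonitis, hepatitis, nephritis and hypophysitis. The general irAE table immediately before those paragraphs is the nearer referent.
- **That the 125 mg should simply be deleted.** Appendix 4 relies on a separate ECI guidance document that is not available here, so the intended dose is unknown.

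**Conclusion.** The safety instructions are inconsistent and wrong as written. The clearest fault is at a first Grade 3 enterocolitis or colitis, where 6.5.1.1 is the outlier, one text against three, on whether pembrolizumab may resume. The Grade 2 colitis texts differ on when steroids start and on what happens after one week, and the Grade 3 steroid texts differ on whether 125 mg IV comes first. The hepatic Grade 2 line is ambiguous. Its 1.8- to 3.6-fold gap rests on an assumed 70 kg and on reading 125 mg as a daily dose. The documents do not show which steroid doses are intended or how many patients would be affected. Sample size, power and the primary analysis do not change. The correction should be made because it is specific and cheap.

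**What to change.** 1. **Section 6.5.1.1, Grade 3, pembrolizumab.** Replace permanent discontinuation with: withhold; restart or discontinue according to the 6.3.8 table; discontinue permanently for Grade 4 or recurrent Grade 3.
2. **Colitis steroids.** The clinical lead confirms one Grade 2 trigger and dose and one Grade 3 regimen against the ECI guidance document. Section 6.5.1.1 then refers to Appendix 4 for steroids and to 6.3.8 for pembrolizumab. Confirmation must come first, because referring to Appendix 4 as it stands would put 125 mg IV ahead of the 1 to 2 mg/kg/day now in 6.5.1.1 for Grade 3. Keep the early anti-diarrhoeal treatment, monitoring, infection work-up and fluid advice in 6.5.1.1. Drop its reference to an Appendix 5, since the appendices run from 1 to 4.
3. **Hepatic Grade 2.** The clinical lead confirms the intended dose against the same document. The line then states one dose, with drug, route and frequency.

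The cost is wording in one Appendix 4 cell and two bullets of 6.5.1.1, clinical confirmation of the colitis and hepatic doses, and inclusion in a protocol amendment. Under Sections 9.2.2 and 10.7, that means TMG agreement, sponsor approval, ethics review, MHRA review where required, and local R&D submission. No visits, procedures or patients are added.
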